Appendix 5 Clinical Laboratory Tests

The protocol-required clinical laboratory assessments are in the following table:

Laboratory Assessments	Parameters			
Hematology	Platelet count		Mean corpuscular volume (MCV)	White Blood Cell Count with Differential: 
 • Neutrophils • Lymphocytes • Monocytes • Eosinophils • Basophils
	Hemoglobin		Mean corpuscular hemoglobin (MCH)	
	Hematocrit			
	Erythrocytes (RBC)			
Biochemistry	Blood Urea Nitrogen	Potassium	Aspartate aminotransferase	Bilirubin (total)
	Creatinine	Sodium	Alanine aminotransferase	Protein
	Glucose	Calcium	Alkaline phosphatase	Triglycerides
	Uric acid	Chloride	Gamma Glutamyl Transferase	Lipase
	C Reactive Protein		Lactate dehydrogenase	Amylase
Routine Urinalysis	
 • Specific gravity • pH, glucose, protein, blood (hemoglobin), ketones, bilirubin, urobilinogen, nitrite, leukocyte esterase by dipstick • Microscopic examination (if blood or protein is abnormal/dipstick is positive for blood or protein). 
Note: In case of a positive result for hemoglobin, leukocyte esterase, protein or nitrite, a flow cytometry count and classification will be performed.
			
Coagulation	
 • Prothrombin Intl. Normalized Ratio • Activated Partial Thromboplastin Time 			
Pregnancy Testing	
 • Serum human chorionic gonadotropin pregnancy test at all time points listed in the SoA (see Section 1.3) 			
Other Screening Tests	
 • Follicle Stimulating Hormone (postmenopausal women only) • Urine drug screen (to include at minimum: Amphetamine, Methamphetamine, barbiturates, 3,4-methylenedioxymethamphetamine, cocaine, opiates, cannabinoids, Benzodiazepine, methadone, phencyclidine, oxycodone, and tricyclic antidepressants): Screening and Day 1 • Serology (HIV-1 Antibody, HIV-2 Antibody, Hepatitis B Virus Surface Antigen, Hepatitis B Virus Core Antibody, Hepatitis C Virus Antibody, QuantiFERON® Test) • SARS-CoV-2 Antigen (rapid test) at Screening and SARS-CoV-2 RNA (PCR) at admission on Day -1 • Thyroid stimulating Hormone • Alcohol breath test: Screening and Day -1 
Estimated Glomerular Filtration Rate based on Chronic Kidney Disease Epidemiology Collaboration Creatinine Equation (2009). All study-required laboratory assessments will be performed by a central laboratory (i.e., PPD clinical laboratory).
			

HIV=human immunodeficiency virus, PCR=polymerase chain reaction, RNA=ribonucleic acid, SARS-CoV-2=severe acute respiratory syndrome coronavirus type 2, RBC=red blood cell count, SoA=Schedule of Assessments.

CCI

Appendix 7 Protocol Amendment History

The information for the current amendment is on the title page.

Protocol Version 2.0 (30 June 2022)

Overall Rationale for the Amendment

This protocol amendment was requested by the German competent authority. On this occasion, an additional clinical laboratory test was added as this was missing in protocol v1.0.

Section # and Name	Description of Change	Brief Rationale
1.3 Schedule of Activities	A 24-hour Holter ECG was added for participants above 45 years of age at screening (see Section 5.2).	For clarification of the ECG measurement at Screening.
1.3 Schedule of Activities 12-Lead ECG	In the notes added, that on Day -1, at predose to COC administration on Day 1, an ECG measurement will be done. On Day 14, at predose to COC administration on Day 15, an ECG measurement was added. On COC administration Days 1 and 15, an ECG measurement was added at 2 hours \pm 30 min postdose.	For clarification of ECG measurements on COC administration days.
1.3 Schedule of Activities Vital Signs	Rewording of note for vital signs measurement.	For clarification.
5.2 Exclusion Criteria	Exclusion criterion was added: '24-hour Holter ECG at screening for participants above 45 years of age showing clinically relevant abnormalities.'	For clarification of the ECG measurement at Screening.
6.1 Study Intervention(s) Administration	Timing of meals on Day 15: 'and the breakfast should be consumed within 25 to 30 minutes' was reworded to 'and the breakfast should be consumed within 30 minutes'.	For clarification. The evobrutinib predose pharmacokinetic sample on Day 15 shall be taken as close as possible to the planned dosing (within 5 min prior to dosing). Thus, for logistical reasons, the time period for the breakfast was adapted.
	Timing of meals on Day 1: 'The breakfast should be consumed within 25 to 30 min.' was reworded to 'The breakfast should be consumed within 30 min.'	For alignment with timing of meals on Day 15.
8.2.2 Vital Signs	'weight and height (at baseline only)' was reworded to 'weight and height (at Screening only)'	For consistency with the wording in Section 1.3 Schedule of Assessments.
8.2.3 Electrocardiograms	A bullet point was added:	For clarification of the ECG measurement at Screening.

**Evobrutinib (M2951) Effect of Evobrutinib on Pharmacokinetics of a Combined Oral
MS200527_0079 Contraceptive**

Section # and Name	Description of Change	Brief Rationale
	'A 24-hour Holter ECG will be obtained at Screening for participants above 45 years of age. This Holter ECG will be reviewed prior to treatment start.'	
8.4 Pharmacokinetics	Table with accepted time deviations from planned PK sampling times: Time window allowance at predose was specified for Days 1, 4, and 15: Day 1: - 60 min Day 4: - 60 min Day 15: -5 min	For clarification of predose time window.
Appendix 5 Clinical Laboratory Tests (Hematology Parameters)	Adding 'Erythrocytes (RBC)' to hematology parameters.	For completion of the safety laboratory parameters. Red blood cell count (erythrocytes) was measured in all safety laboratory tests as part of the hematology panel but this was not stated in the protocol version v1.0.

UCI	Upper Limit of Confidence Interval

3 Modification History

Unique Identifier for Version	Date of IAP Version	Author	Changes from the Previous Version
Final 1.0	13-SEP-2022	PPD	Initial version.

4 Purpose of the Integrated Analysis Plan

The purpose of this IAP is to document technical and detailed specifications for the final analysis of data collected for protocol MS200527_0079. Results of the analyses described in this IAP will be included in the CSR. Additionally, the planned analyses identified in this IAP may be included in regulatory submissions or future manuscripts. Any post-hoc, or unplanned analyses performed to provide results for inclusion in the CSR but not identified in this prospective IAP will be clearly identified in the CSR.

The IAP is based upon Section 9 (Statistical considerations) of the study protocol and protocol amendments and is prepared in compliance with ICH E9. It describes analyses planned in the protocol and protocol amendments.

The wording used in this IAP is chosen to best match the respective wording in the study protocol template, the CSR template, CDISC requirements and special requirements for table layouts. Therefore, the following approach is used:

Generally, the term ‘participant’ will be used instead of ‘subject’ or ‘patient’. However, in tables and listings the term ‘subject’ will be used to match CDISC requirements, except for in-text tables where ‘participant’ will be used to match the CSR and protocol templates. Similarly, the term ‘study intervention’ will be used in this document instead of ‘treatment’ to match protocol and CSR templates, however, tables and listings will use ‘treatment’ for brevity reasons. Exceptions from this rule are commonly used terms like “on-treatment”, “treatment-emergent”, “treatment policy”, “subject-years”, “by-subject”, or names of eCRF pages like “Treatment Termination” page.

5 Objectives and Endpoints

Objectives	Endpoints	Ref. #
Primary		
To investigate the effect of multiple doses of evobrutinib on EE/NET PK in healthy participants	Plasma EE/NET: $AUC_{0-\infty}$ C_{max}	1

Objectives	Endpoints	Ref. #
Secondary		
To assess the safety and tolerability of evobrutinib when administered together with EE/NET in healthy participants	Nature, occurrence, and severity of TEAEs Absolute values and changes in safety laboratory tests Single 12-lead ECGs evaluated by Investigator Vital signs assessed from time of first dose to end of study participation	2 3 4 5
To characterize the effect of evobrutinib on EE/NET PK	Plasma EE/NET: t_{max} $t_{1/2}$ $AUC_{0-tlast}$ CL/F VZ/F	6

6 Overview of Planned Analyses

The final, planned analyses identified in the CSP and in this IAP will be performed after the last participant has completed the last visit and after all data queries resolved as well as the database locked.

A data review meeting will be held prior to database lock for the final analysis. In addition, no database can be locked until this IAP has been approved.

7 Changes to the Planned Analyses in the Clinical Study Protocol

Not applicable.

8 Analysis Sets and Subgroups

8.1 Definition of Analysis Sets

Analysis Set	Description
SCR	All participants, who provided informed consent, regardless of the participant's enrollment and study intervention status in the study.
SAF	All participants, who were administered any dose of any study intervention. Analyses will consider participants as treated.
PK	
The PK Analysis Set is a subset of the SAF, and the PK population will include all participants:
 
• Who have completed the study without any relevant protocol deviations and factors likely to affect the comparability of PK results.• With adequate study intervention compliance.• With evaluable PK data, i.e., no missing values for primary endpoints at each PK profile/assessment day (Day 1, Day 15). 
If participants received prohibited concomitant therapy or medicines, as specified in Section 6.8 in the CSP, they will be excluded from the PK population.
 
All PK analyses will be based on this analysis set.

PK=pharmacokinetics; SAF=safety; SCR=Screening.

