4.4 End of Study Definition

The end of the study is defined as the date of last contact (related to this study) with the last participant who participates in this study (last participant's Safety Follow-up Assessment/Early Termination Assessment).

A participant has completed the study if she has completed all study parts, including the Safety Follow-up Assessment shown in Section 1.3.

Study termination criteria

The study will be discontinued or terminated if:

- Unacceptable risk, any relevant toxicity, or a negative change in the risk/benefit assessment is identified. This might include the occurrence of AEs which character, severity or frequency is new in comparison to the existing risk profile.
- One serious unexpected AE suspected to be drug related occurs or $\geq 50\%$ of the participants show AEs of at least moderate severity for which a causal relationship to the study intervention or study-related procedures cannot be excluded.
- Any data derived from other clinical trials or toxicological studies become available which negatively influence the risk/benefit assessment.

General information on study termination is specified in [Appendix 2](#).

5 Study Population

The criteria in Sections 5.1 and 5.2 are designed to enroll only participants, who are appropriate for the study; thereby, ensuring the study fulfills its objectives. All relevant medical and nonmedical conditions are considered when deciding whether a participant is suitable for this study.

Prospective approval of protocol deviations to inclusion and exclusion criteria, also known as protocol waivers or exemptions, is not permitted. Minor, not clinically relevant excursions (from the normal range) in laboratory findings are allowed at the discretion of the Investigator (see Section 5.2, #16).

Before performing any study assessments that are not part of the participant's routine medical care, the Investigator will confirm that the participant has provided written informed consent, as indicated in [Appendix 2](#).

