9.3 Analyses Sets

The analysis sets are specified below.

The final decision to exclude participants from any analysis population will be made during a data review meeting prior to database lock.

Table 3 Analysis Sets

Analysis Set	Description
Screening (SCR)	All participants, who provided informed consent, regardless of the participant's enrollment and study intervention status in the study.
Safety (SAF)	All participants, who were administered any dose of any study intervention. Analyses will consider participants as treated.
Pharmacokinetic (PK)	
The PK Analysis Set is a subset of the SAF, and the PK population will include all participants:
 
Who have completed the study without any relevant protocol deviations and factors likely to affect the comparability of PK results.With adequate study intervention compliance.With evaluable PK data, i.e., no missing values for primary endpoints at each PK profile/assessment day (Day 1, Day 15). 
If participants received prohibited concomitant therapy or medicines, as specified in Section 6.8, they will be excluded from the PK population.
 
All PK analyses will be based on this analysis set.

PK = Pharmacokinetic; SAF = Safety; SCR = Screening.

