10.2.2 Reasons Leading to the Exclusion from an Analysis Set

If participants are excluded from the PK Analysis Set, the reasons for exclusion will be listed.

Reasons for excluding individual PK concentrations will also be listed separately and flagged in the main listing.

11 Demographics and Other Baseline Characteristics

Demographics and baseline characteristics will be presented for the SAF.

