16.1 Pharmacokinetics

PK evaluation will be performed by Nuvisan GmbH.

All statistical analyses and descriptive summaries of PK data will be performed on the PK Analysis Set.

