16.1.4 General Specifications for PK Concentration and PK Parameter Data

Predose samples that occur before the first drug administration will be assigned a time of 0 hours, as if the sample had been taken simultaneously with the study intervention administration. Same applies to the predose sample after multiple doses.

Predose or trough samples which have been taken after the subsequent dosing will be reported as a protocol deviation. The resulting concentrations will be included in concentration listings but excluded from descriptive statistics of concentrations and from PK parameter estimation.

Values BLQ will be taken as zero for summary statistics of PK concentration data, PK parameter estimation (e.g., AUC) and for graphical presentations.

Missing concentrations (e.g., no sample, insufficient sample volume for analysis, no result or result not valid) will be reported generally as “N.R.”. A participant who withdraws prior to the last planned observation will be included in the analyses up to the time of discontinuation if still included in the PK analysis set.

If samples are collected outside of 10% of the PK sampling time windows defined in the CSP in Section 8.4, these will be included in the PK parameter estimation (NCA) but will be excluded from the concentration summary and mean/median concentration plots.

PK concentrations which are erroneous due to a sampling processing or analytical error (as documented in the bioanalytical report) may be excluded from the PK analysis if agreed by the Sponsor. In this case the rationale for exclusion will be provided in the CSR. Any other PK concentrations that appear implausible to the Clinical Pharmacologist/Clinical PK/PD Scientist will not be excluded from the analysis. Any implausible data will be documented in the CSR.

If important protocol deviations occurred likely to affect the PK profile of participants as specified in Section 10.2.1, the impacted concentrations and PK parameters will be excluded from summary statistics and further statistical evaluation.

Any PK concentrations or PK parameters excluded from summary statistics will be included in participants listings and flagged; a reason for exclusion will be detailed in the CSR (e.g., a footnote or a table of exclusions). Any flags will be included in the study specific CDISC data sets.

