- AUC from time t_{last} extrapolated to infinity given as percentage of AUC_{0-∞}. (AUC_{extra%})

- Span ratio of interval over which $t_{1/2}$ was estimated/ $t_{1/2}$

The regression analysis should contain data from at least 3 different time points in the terminal phase consistent with the assessment of a straight line on the log-transformed scale. Phoenix WinNonlin “best fit” methodology will be used as standard. If warranted, further adjustment may be made by the pharmacokineticist, after agreement with the Sponsor. The last quantifiable concentration $>$ LLOQ should always be included in the regression analysis, while the concentration at t_{max} and any concentrations BLQ which occur after the last quantifiable data point $>$ LLOQ should not be used.

If $AUC_{extra\%} > 20\%$ and/or the coefficient of correlation (Rsq adj) of λ_z is < 0.8 and/or the observation period over which the regression line is estimated (span ratio) is less than 2-fold the resulting $t_{1/2}$, the rate constants and all derived parameters (e.g. $t_{1/2}$, $AUC_{0-\infty}$, CL/F, etc.) will be listed, flagged and included in the parameter outputs. Should more than 10% of subjects be flagged for AUC_{extra} and/or Rsq adj (for a particular analyte), a sensitivity analysis excluding flagged parameters may be performed after discussion with the Sponsor.

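### One primary PK value that cannot be derived removes a participant from all six EE/NET comparisons, even where her other Day 15/Day 1 pairs are valid

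*SAP*

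**What the plan says.** SAP 8.1 and Protocol 9.3 (Table 3) give the same definition of the PK Analysis Set. A participant must have completed the study without relevant deviations, have adequate compliance, and satisfy "With evaluable PK data, i.e., no missing values for primary endpoints at each PK profile/assessment day (Day 1, Day 15". Use of prohibited medication also excludes her. The primary endpoints are AUC0-∞ and Cmax, each for EE and NET (Protocol 3, SAP 5).

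No analyte-specific or parameter-specific set exists. The protocol says "All PK analyses will be based on this analysis set", and SAP 16.1 says "All statistical analyses and descriptive summaries of PK data will be performed on the PK Analysis Set". SAP 16.1.3 fits the same model to Cmax, AUC0-∞ and the secondary AUC0-tlast. Listings of individual concentrations and parameters use the Safety Analysis Set (SAP 16.1.6.1).

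The SAP also provides for exclusion of single values. After an important deviation likely to affect the PK profile, "the impacted concentrations and PK parameters will be excluded from summary statistics and further statistical evaluation" (SAP 16.1.4). SAP 10.2.2 deals with participant exclusions first and then adds: "Reasons for excluding individual PK concentrations will also be listed separately and flagged in the main listing".

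**The concern.** The completeness condition works on the participant, while the analyses work on one parameter of one analyte at a time. A participant whose EE AUC0-∞ cannot be derived on Day 15 may still have valid Day 15/Day 1 pairs for EE Cmax and for every NET parameter. Under the written rule those pairs leave the models and the descriptive tables as well.

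Enrolment is capped at 20 and participants who withdraw are not replaced (Protocol 1.1, 7.2), so pairs lost in this way are not made up. The 90% CIs for the Day 15/Day 1 ratios are the study's main output. What is at stake is their precision in comparisons that the loss did not touch.

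A smaller question of wording follows. The SAP does not say whether a primary parameter excluded under 16.1.4 counts as missing under 8.1. If it does, a value-level exclusion becomes the exclusion of a participant.

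**Working it through.** **No figure in the plan to reproduce.** The sample-size section (Protocol 9.2) is redacted. The check therefore uses the stated maximum of 20 participants, the 90% confidence level in SAP 16.1.3, and assumed within-participant CVs.

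**Step 1: values required.** 2 primary parameters × 2 analytes × 2 days = 8 values per participant, all of which must be present.

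**Step 2: comparisons affected.** The model is fitted to 3 parameters (Cmax, AUC0-∞, AUC0-tlast) × 2 analytes = 6 comparisons. Suppose one participant's EE AUC0-∞ cannot be derived on one day. The rule removes her from all 6. The other 5 can still be calculated, or 4 if her EE AUC0-tlast is judged not comparable.

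**Step 3: how this could happen.**
- SAP 16.1.5.1 says "The regression analysis should contain data from at least 3 different time points in the terminal phase", and the concentration at tmax may not be used. With fewer usable points AUC0-∞ may not be derivable, although Cmax is observed.
- An assay failure could affect one analyte only.
- A poor fit is not a trigger. AUC0-∞ with more than 20% extrapolation, adjusted R² below 0.8 or a span ratio below 2 is flagged and kept (SAP 16.1.5.1).
- A lost sample usually affects both analytes, because one blood sample serves EE and NET (Protocol 8.4). When a loss affects both analytes and all parameters, nothing can be recovered.

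**Step 4: cost per comparison.** With complete pairs, the model with fixed treatment and random subject gives the paired-t interval. The log-scale half-width is t(0.95, n−1) × √(2/n) × s, where s = √ln(1+CV²). Relative to n=20, s cancels:

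- n=20: 1.7291/√20 = 0.3866
- n=19: 1.7341/√19 = 0.3978; ratio 1.0289, so 2.9% wider
- n=18: 1.7396/√18 = 0.4100; ratio 1.0605 (1.06048 before rounding), so 6.0% wider

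**Step 5: on the ratio scale.** The upper limit as a multiple of the point estimate is exp(half-width):

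| Assumed CV | n=20 | n=19 | n=18 |
|---|---|---|---|
| 15% | 1.0850 | 1.0875 | 1.0903 |
| 20% | 1.1144 | 1.1179 | 1.1217 |
| 30% | 1.1741 | 1.1796 | 1.1856 |

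**The case against.** The strongest reply is that this is a deliberate complete-case rule. The protocol and SAP state it identically and apply it consistently, and it keeps every comparison on the same participants. That advantage is real, and the fix gives it up. The documents do not offer it as a reason, however, and in a study this small it does not clearly outweigh dropping valid pairs.

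The second reply is that the trigger is nearly empty. Participants are resident, sampling runs to 72 hours, poor fits are kept and the two analytes share a sample. This stands, and it is why the point is minor. The documents give neither a loss rate nor the assay limit.

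The third reply is that the SAP's structure already answers the question about excluded values. SAP 10.2.1, 10.2.2 and 16.1.4 separate value-level from participant-level exclusion, which would have little purpose if the first always led to the second. This largely stands. A clarifying sentence is missing, not a method.

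A reader might infer three stronger points that the documents do not support:

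- *A large loss of participants.* Treating the eight values as independently missing at an assumed 2% gives 0.98⁸ = 85.1% retained, or 17.0 of 20. The 2% has no source in the documents, and independence likely overstates the loss because missing values cluster within a participant.
- *A contradiction over withdrawals.* SAP 16.1.4 says that a participant who withdraws early "will be included in the analyses up to the time of discontinuation if still included in the PK analysis set". The clause is expressly subject to membership of the set, so it contradicts nothing and changes no result, even if only completers qualify.
- *A need to relax the completer condition.* Protocol 4.4 says "A participant has completed the study if she has completed all study parts, including the Safety Follow-up Assessment shown in Section 1.3", which is strict. But removing the condition would change the analysis population. It could admit Day 15 profiles cut short, whose heavily extrapolated AUC0-∞ would be kept.

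**Conclusion.** The point holds as a cheap improvement. Read as written, SAP 8.1 and Protocol 9.3 let one underivable primary parameter of one analyte remove valid pairs from up to five other comparisons. Inclusion by parameter would keep them.

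The gain is precision only. For each comparison affected, it avoids a half-width 2.9% wider when one of 20 participants is lost and 6.0% wider when two are lost. At an assumed CV of 20%, one loss moves the upper factor from 1.1144 to 1.1179. The percentages assume that all 20 participants would otherwise contribute complete pairs. The ratio-scale factors also depend on the assumed CVs. How often the rule would apply cannot be estimated from the documents.

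No effect on bias, type I error or power is claimed. Protocol 9.1 makes the analysis descriptive, and SAP 9.4 assumes that data are missing completely at random. Under that assumption the complete-case rule loses precision without introducing bias.

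**What to change.** 1. In SAP 8.1 and Protocol 9.3, replace the third condition with: *With at least one primary parameter of EE or NET evaluable on both Day 1 and Day 15.*
2. Add to SAP 16.1.3: *For each analyte and parameter, the model includes every PK-set participant with a valid value on both Day 1 and Day 15; a missing or excluded value removes the participant from the analysis of that parameter only.* Show n for each modelled comparison; the descriptive parameter tables already report it (SAP 16.1.2).
3. As a supporting clarification in SAP 16.1.4, state that set membership is decided first and that an excluded value then counts as missing for that parameter only.

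Keep the completer, relevant-deviation, compliance and prohibited-medication conditions as written.

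The cost is wording only, with no additional data or participants. If the protocol is not amended, record the change in SAP Section 7. The downside is that n may differ between comparisons, so they may not rest on identical participants. If the sponsor prefers the single common set, it should give its reason and state whether an excluded value counts as missing under 8.1, because that decides n.
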